7.3 LOST TO FOLLOW-UP

A participant will be considered lost to follow-up if he or she fails to return for the 24 month visit and is unable to be contacted by the study site staff.

The following actions must be taken if a participant fails to return to the clinic for a required study visit:

- The site will attempt to contact the participant and reschedule the missed visit within 10 days and counsel the participant on the importance of maintaining the assigned visit schedule and ascertain if the participant wishes to and/or should continue in the study.
- Before a participant is deemed lost to follow-up, the investigator or designee will make every effort to regain contact with the participant (where possible, 3 telephone calls and, if necessary, a certified letter to the participant's last known mailing address or local equivalent methods). These contact attempts should be documented in the participant's medical record or study file.
- Should the participant continue to be unreachable, he or she will be considered to have withdrawn from the study with a primary reason of lost to follow-up.

8 STUDY ASSESSMENTS AND PROCEDURES

8.1 EFFICACY ASSESSMENTS

- **Physical examination (all visits)**
 - Presence/absence of reinjury
 - Return to Dance status
 - Adherence to PT and/or SuperBetter app exercises
 - Type of dance
 - Hours of dance per week
- **Administration of questionnaires (all visits)**
 - PROMIS + PROMIS mental health
 - SCS
 - FAAM

The **Self Compassion Scale (SCS)** is a validated measure of self-compassion in individuals, which is a concept or trait associated with psychological wellbeing including, potentially, lower depression and anxiety (7). It asks patients questions about their self-kindness or, conversely, self-judgment during everyday times of difficulty. We will be using the short form version which has been shown to be an economical alternative to the long Self Compassion Scale, saving time for subjects by reducing the length of the questionnaire by half, while still being reliable (16). This survey will take approximately 5 minutes to complete.

The **Foot and Ankle Ability Measure (FAAM)** is a validated measure of physical function for a broad range of musculoskeletal conditions of the lower leg, foot, and ankle (17). It asks patients questions about their current level of difficulty performing different everyday tasks, activities, and sports motions. This survey will take no more than 10 minutes to complete.

The **Patient-Reported Outcomes Measurement Information System (PROMIS)** is an effective measure seen to be useful in evaluating pain interference in diverse settings, and mental health among musculoskeletal patients (19,20). It asks questions regarding patients' pain interference with activity and daily living, mobility, and current depression and anxiety symptoms. This survey will take no more than 10 minutes to complete.

8.2 SAFETY AND OTHER ASSESSMENTS

Subjects will be assigned exercises within the app by the “host,” which will be managed by the study staff. One activity will be released per day. They will only be sent 5 per week. To mitigate any potential fatigue, discomfort, or distress from the app usage, or questionnaires, we will inform participants that they may leave any survey question blank that they do not wish to answer, and to communicate with us should they feel they need to stop using the app at any time.

8.3 ADVERSE EVENTS AND SERIOUS ADVERSE EVENTS

8.3.1 DEFINITION OF ADVERSE EVENTS (AE)

The FDA definition of an Adverse event is any untoward medical occurrence associated with the use of an intervention in humans, whether or not considered intervention-related (21 CFR 312.32 (a)).

8.3.2 DEFINITION OF SERIOUS ADVERSE EVENTS (SAE)

An adverse event (AE) or suspected adverse reaction is considered "serious" if, in the view of either the investigator or sponsor, it results in any of the following outcomes: death, a life-threatening adverse event, inpatient hospitalization or prolongation of existing hospitalization, a persistent or significant incapacity or substantial disruption of the ability to conduct normal life functions, or a congenital anomaly/birth defect. Important medical events that may not result in death, be life-threatening, or require hospitalization may be considered serious when, based upon appropriate medical judgment, they may jeopardize the participant and may require medical or surgical intervention to prevent one of the outcomes listed in this definition. Examples of such medical events include allergic bronchospasm requiring intensive treatment in an emergency room or at home, blood dyscrasias or convulsions that do not result in inpatient hospitalization, or the development of drug dependency or drug abuse.

8.3.3 CLASSIFICATION OF AN ADVERSE EVENT

8.3.3.1 SEVERITY OF EVENT

The following guidelines will be used to describe severity of AEs:

- **Mild** – Events require minimal or no treatment and do not interfere with the participant’s daily activities.
- **Moderate** – Events result in a low level of inconvenience or concern with the therapeutic measures. Moderate events may cause some interference with functioning.
- **Severe** – Events interrupt a participant’s usual daily activity and may require systemic drug therapy or other treatment. Severe events are usually potentially life-threatening or incapacitating. Of note, the term “severe” does not necessarily equate to “serious”.]

8.3.3.2 RELATIONSHIP TO STUDY INTERVENTION

- **Related** – The AE is known to occur with the study intervention, there is a reasonable possibility that the study intervention caused the AE, or there is a temporal relationship between the study

intervention and event. Reasonable possibility means that there is evidence to suggest a causal relationship between the study intervention and the AE.

- **Not Related** – There is not a reasonable possibility that the administration of the study intervention caused the event, there is no temporal relationship between the study intervention and event onset, or an alternate etiology has been established.

8.3.3.3 EXPECTEDNESS

There are no expected adverse events.

8.3.4 TIME PERIOD AND FREQUENCY FOR EVENT ASSESSMENT AND FOLLOW-UP

The occurrence of an adverse event (AE) or serious adverse event (SAE) may come to the attention of study personnel during study visits and interviews of a study participant presenting for medical care, or upon review by a study monitor.

All AEs including local and systemic reactions not meeting the criteria for SAEs will be captured on the appropriate case report form (CRF). Information to be collected includes event description, time of onset, clinician's assessment of severity, relationship to study product (assessed only by those with the training and authority to make a diagnosis), and time of resolution/stabilization of the event. All AEs occurring while on study must be documented appropriately regardless of relationship. All AEs will be followed to adequate resolution.

Any medical condition that is present at the time that the participant is screened will be considered as baseline and not reported as an AE. However, if the study participant's condition deteriorates at any time during the study, it will be recorded as an AE.

Changes in the severity of an AE will be documented to allow an assessment of the duration of the event at each level of severity to be performed. AEs characterized as intermittent require documentation of onset and duration of each episode.

The Principal Investigator will record all reportable events with start dates occurring any time after informed consent is obtained until 7 (for non-serious AEs) or 30 days (for SAEs) after the last day of study participation. Events will be followed for outcome information until resolution or stabilization.

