1.2 SCHEMA

1.3 SCHEDULE OF ACTIVITIES (SOA)

Procedures	W	C	L	O	8	≥	Φ	3	E	o	ω	E	o	–	>	Φ	–	∞	E	2	>	Φ	
Informed consent	X																						
Demographic s	X																						
Medical History	X																						
Randomizati on	X																						
Physical Exam	X		X		X		X		X		X		X		X		X		X		X		
Outcomes Scores	X			X		X		X		X		X		X		X		X		X		X	
Standard PT activities	X		X		X*																		
App intervention (treatment group only)	X		X		X																		

*= Additional PT up to 12 weeks/3months may or may not be ordered by the treating physician for both the treatment group and observation group depending on the recovery of the subject's foot and/or ankle injury

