6 STUDY INTERVENTION

6.1 STUDY INTERVENTION(S) ADMINISTRATION

6.1.1 STUDY INTERVENTION DESCRIPTION

The study intervention will be mental health exercises via the SuperBetter app for dancers participating in PT rehab for foot or ankle injuries. The control will be PT rehab only, without implementation of the SuperBetter app.

Subjects who enroll and are randomized into the treatment arm will be assisted in clinic to log into the app SuperBetter. They will be added to the group run by the “host”/study staff. The SuperBetter app offers a daily exercise on a schedule that will be managed by the “host” or study staff. Subject will complete 1 full activity per day. This activity will not exceed 15 minutes in total including app boot-up, but the full activity itself will not exceed 10. These activities ask participants to practice different exercises that might be found in Cognitive Behavioral Therapy, such as mindfulness. They are framed like a game for engagement, where the subject can “get a power up” when they take 30 seconds to breathe deeply and think of 3 loved ones, as an example. 1 full daily activity is constituted by 4 to 6 very brief activities similar to the previously described.

Both groups will undergo physical exams at their normally scheduled orthopedic appointments at baseline, 8 weeks, 3 months, 6 months, 12 months, 18 months, and 24 months where presence/absence of reinjury, return to dance, adherence to PT and/or the SuperBetter app, type(s) of dance, and hours of dance per week will be assessed. Both groups will be asked to complete the PROMIS, SCS, and FAAM at baseline, 3-, 6-, 12-, 18-, and 24 months.

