6.4 STUDY INTERVENTION COMPLIANCE

Email reminders will be sent through the app by the study team to remind the subject to complete their exercise(s). Subjects in the study group will be asked if they have been participating in the app usage and/or PT exercises prescribed at their clinic visits. The study staff will serve as a "host," and new treatment arm participants will be added to a group that is managed by the "host"/study staff. The host account has the capability to see whether a participant has completed daily exercise(s) or not. Noncompliance will be determined as a subject not registering in the app, or not using the app at all. If a subject is using the app less than prescribed, they will still be included but we will make note of their number of activities completed and will verbally inquire about their app usage at their following clinic visit.

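### All adverse events must be documented, but no visit procedure asks for them; counts other than reinjury may be incomplete and may not be comparable between arms

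*Protocol*

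**What the plan says.** **The duty.** Protocol 8.3.4 states: "All AEs occurring while on study must be documented appropriately regardless of relationship". It also asks for onset, severity and its changes, relationship, resolution, and the onset and duration of each episode of an intermittent event.

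**The method.** The same section says that events "may come to the attention of study personnel during study visits and interviews of a study participant presenting for medical care", or may be noticed when a monitor reviews the study. It describes no question put to participants.

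**The visits.** Section 6.1.1 describes physical exams for both groups "where presence/absence of reinjury, return to dance, adherence to PT and/or the SuperBetter app, type(s) of dance, and hours of dance per week" are assessed. Section 8.1 repeats that list and adds the questionnaires. The rows of the schedule in 1.3 are consent, demographics, history, randomization, exam, outcome scores, physical therapy and app use.

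**App-arm contacts.** Section 6.4 says "Subjects in the study group will be asked if they have been participating in the app usage" or the prescribed PT exercises, with a further verbal inquiry when app use is low. Section 8.2 invites participants to "communicate with us should they feel they need to stop using the app at any time". Section 4.1 provides for monitoring of safe app use, and 7.1 for an examination and injury data when the app is discontinued.

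**Reporting.** Section 9.3 defines a safety population for reporting adverse events and reinjury. Section 9.4.4 says that safety analyses do not apply.

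**The concern.** A duty to record everything needs a procedure that looks for everything. Without one, what is recorded depends on what a participant volunteers and on how often staff happen to talk with that participant. The first dependence makes the record incomplete. The second can make it unequal between arms, because app users have occasions for contact that controls do not have, and everyone knows the allocation.

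The event most exposed is emotional distress from the app or the questionnaires. The protocol itself names this risk (2.3.1, 8.3.5, 8.3.7), in participants aged 13 to 18. If distress is noted more readily in app users, adverse event counts listed by arm would be read as a property of the app when they partly reflect who was spoken to.

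**Working it through.** The documents state no adverse event rate, detection rate or safety sample size, so there is no figure to reproduce. The check is mainly a comparison of sections.

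**1. Is there an adverse event inquiry anywhere in the visit procedures?**
- Schedule (1.3): no row.
- Visit descriptions (6.1.1, 8.1): none.
- Safety assessments (8.2): limits on app activities, permission to skip survey items, and the invitation to get in touch about stopping the app. No inquiry.
- Section 8.3.4: places where an event might come to light. No inquiry.

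**2. What is collected equally in both arms?**
- "Presence/absence of reinjury" is an item of the scheduled exams (8.1). Reinjury is therefore covered.
- PROMIS covers "current depression and anxiety symptoms" (8.1). It is only a partial safeguard: it asks about the current state, items may be skipped (2.3.1, 8.2), and no score or answer is defined as an adverse event. Under 6.1.1 the first administration after baseline is at 3 months, about when the 12-week app period ends.
- Section 8.3.7 tells families to contact the care team about distress from questionnaires or app. It is not limited to one arm, but it relies on the family to act.

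**3. What exists in effect only for app users?** Safe-use monitoring (4.1), verbal inquiry about low use (6.4), the examination at app discontinuation (7.1) and the invitation about stopping the app (8.2).

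**4. How far apart are the occasions?** Exams fall at baseline, 8 weeks, and 3, 6, 12, 18 and 24 months (6.1.1). After month 3 the gaps are 3, 6, 6 and 6 months. Episode-level onset and duration are unlikely to be complete over such gaps unless someone asks.

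**5. Could this distort a comparison?** Illustration only. Let the expected number of participants with a recorded event be n × true risk × probability of detection. Assume n = 50 / 2 = 25 per arm (the total of 50 is from 9.2; the equal split is an assumption) and the same true risk in both arms.

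| True risk (assumed) | Detection, control / app (assumed) | Control | App | Ratio |
|---|---|---|---|---|
| 20% | 100% / 100% | 25 × 0.20 × 1.00 = 5.0 | 5.0 | 1.0 |
| 20% | 50% / 50% | 25 × 0.20 × 0.50 = 2.5 | 2.5 | 1.0 |
| 20% | 50% / 80% | 2.5 | 25 × 0.20 × 0.80 = 4.0 | 1.6 |
| 20% | 30% / 90% | 25 × 0.20 × 0.30 = 1.5 | 25 × 0.20 × 0.90 = 4.5 | 3.0 |
| 10% | 50% / 80% | 1.25 | 2.0 | 1.6 |
| 10% | 30% / 90% | 0.75 | 2.25 | 3.0 |
| 40% | 50% / 80% | 5.0 | 8.0 | 1.6 |
| 40% | 30% / 90% | 3.0 | 9.0 | 3.0 |

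Sample size and true risk cancel, so the ratio is simply the ratio of the assumed detection probabilities. The table shows the mechanism: equal under-detection gives incomplete but comparable counts, and only unequal detection biases the comparison. It is not evidence of how large the inequality is.

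**The case against.** The strongest case against runs as follows.

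- **Controls are not left without a prompt.** A reader might infer that they are, but 8.3.7 covers questionnaire distress in both arms and 8.3.5 requires such distress to be documented. This stands. The remaining weakness is that the route is passive.
- **The most relevant harms are already measured alike.** This stands fully for reinjury. It stands in part for emotional symptoms, because nothing links PROMIS to the adverse event record.
- **The app contacts are not described as adverse event routes.** Section 6.4 is a compliance question that also mentions PT exercises, adherence is assessed at visits in both arms, and monitoring app safety only among app users follows from the design. This stands: unequal capture is a reasoned inference and is not stated in the protocol.
- **No planned analysis is harmed.** Section 9.4.4 specifies none, and there is no between-arm adverse event test, estimate or stopping rule. This stands for formal analysis. Events reported for the 9.3 safety population, if shown by arm, would still be compared by eye.
- **Section 8.3.4 does not exclude asking, and the question may sit in a visit worksheet or manual of procedures that is not shown.** This is possible. But the protocol expects no adverse events (8.3.3.3) and calls safety analyses inapplicable, so one should not rely on staff to add the question unprompted.

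**Conclusion.** The concern holds in a limited form. The mismatch between a duty to document everything and a purely passive description of detection is plain from 8.3.4, 1.3, 6.1.1 and 8.1, and needs no assumption beyond there being no question in documents that are not shown. The further step, that counts of events other than reinjury may not be comparable between arms, rests on the inference that extra app-arm contacts in an unblinded trial raise the chance of an event being noted.

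A reader might go further and conclude that the counts are in fact not comparable, or that distress would appear some definite multiple more often in the app arm. The documents support neither: they contain no detection rates, and any multiple only returns the rates assumed. The size of any difference is unknown and could be nil.

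The point does not touch the primary endpoint. It is a cheap improvement to safety capture in a study of adolescents.

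**What to change.** - Add an adverse event row to the schedule in 1.3 and an item to 8.1: one open question, in the same words, asked of both arms at every scheduled visit.
- Record for each event whether it was solicited or volunteered. Tabulate separately those that surfaced only through app contacts, and base any side-by-side reading of the arms on the solicited reports.
- Reconcile 9.3, which reports adverse events in a safety population, with 9.4.4, which says safety analyses do not apply. A descriptive table by arm would be enough.

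Cost: one line on an existing worksheet. At an assumed minute per visit, with six exams after baseline (6.1.1) and 50 participants, this is 6 × 50 × 1 = 300 minutes over the whole trial. The downside is that more minor events will be recorded.

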8.3.5 ADVERSE EVENT REPORTING

Since this study is applying mental health exercises, there are not potential adverse events as there may be in an experimental drug study. Any complications that arise, such as emotional distress from the app or questionnaires, will be documented in the study database and in the subject's medical record and will be treated according to standard of care. There may be a remote possibility that an unforeseen adverse event could occur which would be reported to the IRB.

8.3.6 SERIOUS ADVERSE EVENT REPORTING

As this is a minimal-risk study in healthy children, and there is no study drug or device, SAEs are not expected. However, should an SAE occur, it would be followed until satisfactory resolution or until the site investigator deems the event to be chronic or the participant is stable. It will be reported to the IRB as soon as possible, but in no event later than 10 working days after the investigator first learns of the effect.

8.3.7 REPORTING EVENTS TO PARTICIPANTS

Families will be notified of any SAEs, including, but not limited to, emotional distress or discomfort as a result of the questionnaires and/or app and that if that occurs they should reach out to their clinical care team.

8.3.8 EVENTS OF SPECIAL INTEREST

Not applicable

8.3.9 REPORTING OF PREGNANCY

Not applicable

8.4 UNANTICIPATED PROBLEMS

8.4.1 DEFINITION OF UNANTICIPATED PROBLEMS (UP)

The Office for Human Research Protections (OHRP) considers unanticipated problems involving risks to participants or others to include, in general, any incident, experience, or outcome that meets all of the following criteria:

- Unexpected in terms of nature, severity, or frequency given (a) the research procedures that are described in the protocol-related documents, such as the Institutional Review Board (IRB)-approved research protocol and informed consent document; and (b) the characteristics of the participant population being studied;
- Related or possibly related to participation in the research (“possibly related” means there is a reasonable possibility that the incident, experience, or outcome may have been caused by the procedures involved in the research); and
- Suggests that the research places participants or others at a greater risk of harm (including physical, psychological, economic, or social harm) than was previously known or recognized.

8.4.2 UNANTICIPATED PROBLEM REPORTING

The investigator will report unanticipated problems (UPs) to the reviewing Institutional Review Board (IRB) and to the Data Coordinating Center (DCC)/lead principal investigator (PI). The UP report will include the following information:

- Protocol identifying information: protocol title and number, PI's name, and the IRB project number;
- A detailed description of the event, incident, experience, or outcome;

- An explanation of the basis for determining that the event, incident, experience, or outcome represents an UP;
- A description of any changes to the protocol or other corrective actions that have been taken or are proposed in response to the UP.

To satisfy the requirement for prompt reporting, UPs will be reported using the following timeline:

- UPs that are serious adverse events (SAEs) will be reported to the IRB within 48 hours of the investigator becoming aware of the event.
- Any other UP will be reported to the IRB within 10 days of the investigator becoming aware of the problem.
- All UPs should be reported to appropriate institutional officials (as required by an institution's written reporting procedures), the supporting agency head (or designee), and the Office for Human Research Protections (OHRP) within 10 days of the IRB's receipt of the report of the problem from the investigator.

8.4.3 REPORTING UNANTICIPATED PROBLEMS TO PARTICIPANTS

Participants in this study will be informed of UPs by one of the physicians working on the study.

9 STATISTICAL CONSIDERATIONS

9.1 STATISTICAL HYPOTHESES

- Primary Efficacy Endpoint(s):
 - Null Hypothesis (H_0): There will be no difference in self compassion scores to return to unrestricted dance at 3 months between the mental health app group and control group.
 - Alternative Hypothesis (H_1): Self compassion and return to unrestricted dance is expected to be improved in the mental health app treatment group compared to control group.
 - Type of Comparison: Superiority
 - Time Point: 12 months
 - Analysis Method: Logistic regression or Fisher's exact test depending on data distribution.
- Secondary Efficacy Endpoint(s):
 - Change in Self-Compassion Scale scores over time (repeated measures ANOVA or nonparametric equivalent) in experimental group compared to control group
 - Association of self-compassion with FAAM and PROMIS scores (correlation/regression)
 - Time to initial return to dance (Kaplan-Meier with log-rank test or Cox regression)
 - Reinjury incidence (descriptive comparison by self-compassion group)

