4 STUDY DESIGN

4.1 OVERALL DESIGN

Null hypothesis (H_0): There will be no difference in self compassion scores to return to unrestricted dance at 3 months between the mental health app group and control group.

Alternative hypothesis (H_1): Self compassion and return to unrestricted dance is expected to be improved in the mental health app treatment group compared to control group.

Patient Enrollment and Randomization: Patients who meet inclusion criteria at this single site will be offered enrollment in this RCT. Enrolled patients will be randomized into one of 2 groups. It will be true randomization without patient preference but will not be blinded. There are no sub-studies or stratifications to be performed within this group.

Trial Interventions: Following randomization, the control group will undergo physical therapy treatment only while the experimental group will also participate in mental health exercises through the app, SuperBetter, for approximately 10 minutes 5 days per week for 12 weeks. All participants will have a minimum order of 8 weeks of physical therapy. At 8 weeks, depending on the individual patient and injury, the doctor may order an additional 4 weeks of PT, for a total of 12. This will be according to the physician's standard of care for their practice and clinical expertise. The number of PT visits ultimately attended by each subject will be recorded. If those in the treatment arm are not prescribed 4 additional weeks of PT at the 8-week time period, they will still use the app for 4 additional weeks for a total of 12 weeks of app usage.

Data collection: All patients in both groups will return to clinic at 3 months, 6 months, 12 months, 18 months, and 24 months. The 24-month visit represents completion of participation in the study. Throughout the trial, patients will be monitored for safe usage and engagement with the mobile app, to determine if they need to stop or limit the intervention.

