9.2 SAMPLE SIZE DETERMINATION

Planned Sample Size and Feasibility

The total number of participants planned for enrollment is 50, which includes a buffer to account for expected attrition.

Outcome Measure Used for Sample Size Calculations

Return to unrestricted dance participation at 12 months, a binary (yes/no) outcome.

Test Statistic

A Fisher's exact test will be used to compare the proportion of participants who return to unrestricted dance between experimental and control groups (dichotomized by a median split or similar method).

Statistical Hypotheses

Null Hypothesis (H_0): There will be no difference in self compassion scores to return to unrestricted dance at 3 months between the mental health app group and control group.

Alternative Hypothesis (H_1): Self compassion and return to unrestricted dance is expected to be improved in the mental health app treatment group compared to control group.

Assumptions for Sample Size Calculation

- Alpha (Type I error rate): 0.05 (two-tailed)
- Power (1 - Beta): 0.80 (80%)
- Effect Size: Odds Ratio (OR) = 5.0
- Expected Proportions:
 - Control group: 60% expected to return to dance
 - Experimental: 95% expected to return to dance
- These assumptions are informed by preliminary data and theoretical rationale suggesting that higher self-compassion is strongly associated with better emotional regulation, adherence to rehabilitation, and psychological resilience—all of which plausibly contribute to better recovery outcomes in dancers (Zarzycki et al., Gennarelli et al., Christino et al.).

Statistical Method and Software

- Sample size was calculated using:
 - Validated using G*Power 3.1 (Faul et al. 2007)
- Using these assumptions, the required sample size is:
 - 38 participants total (19 per group) to detect an OR of 5.0 with 80% power at $\alpha = 0.05$.
- Missing data on the primary endpoint (i.e., return to dance status at 12 months) will be minimized through close follow-up and contact strategies. If missing data occur, analyses will proceed using available-case analysis and sensitivity analyses will be conducted as described in Sections 9.4.2 and 9.4.3.
- Interim Analyses
 - No formal interim analyses are planned due to the small sample size and short duration of primary outcome measurement. Therefore, no statistical correction (e.g., O'Brien-Fleming or Pocock boundaries) is required.
- Sensitivity and Robustness Checks

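### The stated primary hypothesis (3 months, self-compassion mixed with return to dance) is not the endpoint that the protocol sizes and names as primary (return to unrestricted dance at 12 months)

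*Protocol*

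**What the plan says.** Sections 4.1, 9.1 and 9.2 carry the same null hypothesis. In Section 9.1 it is "no difference in self compassion scores to return to unrestricted dance at 3 months between the mental health app group and control group"; in Section 4.1 it begins "There will be no difference in self compassion scores to return to unrestricted dance at 3 months". The alternative joins two outcomes and gives no time: "Self compassion and return to unrestricted dance is expected to be improved in the mental health app treatment group".

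Other statements point elsewhere:

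- **Section 9.1, same block:** "Time Point: 12 months". The analysis method is "Logistic regression or Fisher's exact test depending on data distribution", so only binary-outcome methods are named.
- **Section 9.2, sizing outcome:** "Return to unrestricted dance participation at 12 months, a binary (yes/no) outcome".
- **Section 9.2, missing data:** "Missing data on the primary endpoint (i.e., return to dance status at 12 months". This sentence identifies the primary endpoint.
- **Section 9.2, test statistic:** Fisher's test is to compare "experimental and control groups (dichotomized by a median split or similar method".
- **Sections 1.1 and 3:** return to dance is the primary endpoint, with no time point. Self-compassion is secondary, as it is in 9.1 and 9.4.3.
- **Section 9.4.2:** the primary outcome is binary return to dance, without a time point and without the qualifier that it be unrestricted. The test is Pearson's chi-square, or Fisher's if any cell is below 10. Odds ratios are presented only for significant findings.

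**The concern.** A confirmatory trial needs one primary question fixed before data are seen. Here the formal hypothesis and the operative plan differ in variable and in time point. A result at 12 months would neither reject nor support the null as written, and nothing in the sample size speaks to 3 months or to self-compassion.

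Return to dance is assessed at 3, 6, 12, 18 and 24 months in an unblinded trial, so the inconsistency leaves room to choose the time point after results are known.

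Two further wordings add to the problem. Randomised arms are not formed by a median split; that phrase fits a comparison of high with low self-compassion. Such a comparison is not protected by randomisation: it can show a difference when the app does nothing, and it dilutes the effect when the app works. And an odds ratio shown only when significant leaves a non-significant primary result without its planned effect measure.

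**Working it through.** **1. What the sample size supports.** Inputs from Section 9.2: 60% versus 95%, two-sided alpha 0.05, power 0.80, equal arms. With unpooled variance,

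n = (1.960 + 0.842)² × [0.60×0.40 + 0.95×0.05] / 0.35² = 7.849 × 0.2875 / 0.1225 = 18.4, so 19 per group (38 in total).

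This matches the protocol's figure; the arcsine formula also gives 19. Every input belongs to the 12-month binary endpoint. No 3-month rate and no self-compassion difference or SD enters.

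**2. The intended test with the named method.** Full enumeration, two-sided Fisher, p < 0.05, 60% versus 95%:

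| Evaluable per arm | Power |
|---|---|
| 19 | 68.3% |
| 23 | 79.8% |
| 24 | 82.1% |
| 25 | 82.2% |

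**3. The hypothesis as written.** The protocol gives no 3-month rates, so these are assumptions (Fisher, 25 per arm):

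| Assumed rates, control / app | Gap | Power |
|---|---|---|
| 30/65, 40/75, 50/85 | 35 points | 65.3%, 65.4%, 67.6% |
| 20/40, 30/50, 40/60, 50/70 | 20 points | 23.1%, 23.3%, 23.7%, 23.3% |

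For self-compassion as a continuous score (two-sample t, 25 per arm), 80% power needs a difference of 0.81 SD; power at 0.5 SD is 41%.

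**4. The median split.** Assume that return depends only on arm (60% or 95%), that the app shifts self-compassion by d SD, and that the score is normal with equal variance. With equal arms the pooled median lies at d/2, so a share h = Φ(d/2) of the high half is from the app arm. The high-minus-low difference is 0.35 × (2h − 1):

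| d | h | High half | Low half | Difference |
|---|---|---|---|---|
| 0.2 | 0.540 | 78.9% | 76.1% | 2.8 points |
| 0.5 | 0.599 | 81.0% | 74.0% | 6.9 points |
| 0.8 | 0.655 | 82.9% | 72.1% | 10.9 points |

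The randomised difference is 35 points.

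**5. Error rate.** At 25 per arm, Fisher's actual size is 3.0%, 3.3%, 3.0%, 2.3% and 2.2% for common rates of 0.4, 0.5, 0.6, 0.7 and 0.8. If significance at either 3 or 12 months counted, simulation gives 4.7% to 6.1% (assumed null rates 0.4 to 0.6 at 3 months and 0.6 to 0.8 at 12 months, latent correlation 0.2 to 0.8).

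**6. The odds ratio.** At a true 95%, the chance that all 25 app participants return is 0.95²⁵ = 0.277. In about 28% of trials the sample odds ratio would be infinite.

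**The case against.** The strongest reply is that the intent is clear and the null is merely badly drafted. The endpoint statements, the binary methods, the sizing outcome and the primary analysis all concern return to dance, and the primary objective does say without limitations. That makes 12-month return the better reading, but it does not excuse a different hypothesis written three times. The text is also not all on one side: Section 3 stresses the immediate effect on short-term recovery, and Section 9.2 cites a short primary measurement period to justify having no interim analysis. Both could point to 3 months.

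Section 9.4.2 allows chi-square when every cell is at least 10, so Fisher's figures might seem not to apply. At 25 per arm the two tests give the same decision in every table where chi-square would be used, so size and power are unchanged.

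The error-rate check covers only two time points. Adding an independent 5% self-compassion test to one Fisher test gives 1 − (0.978 × 0.95) = 7.1% to 1 − (0.967 × 0.95) = 8.1%. This is modest, and the case does not rest on it.

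The median-split dilution assumes that return depends only on arm. If self-compassion itself drives recovery, as Section 9.2 argues, the high-low gap would be larger. But it would then partly reflect differences between dancers that exist without the app, so the phrase should still go. It may be leftover text, since Section 9.3 confines median grouping to exploratory subgroups.

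The reporting of odds ratios and the Fisher power at 19 per group are separable issues. They matter here because fixing the primary test brings them into view.

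**Conclusion.** The concern holds and must be fixed. The contradiction in time point and variable is plain in the text, and no section reconciles it. The planned sample size belongs to 12-month return to unrestricted dance. With all 25 per arm evaluable, that test has 82% power if the rates really are 60% and 95%; the hypothesis as written has no sample size behind it. The 3-month powers (65% to 68%, or 23% to 24%) and the median-split gaps (3 to 11 points) rest on assumed values and show scale only. Inflation of the error rate is not the main harm. The main harm is that the trial's formal question and its planned test do not correspond.

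**What to change.** - State one primary null in Sections 4.1, 9.1, 9.2 and 9.4.2: the proportion returned to unrestricted dance at 12 months is equal in the two arms as randomised. Use 12 months because the sizing outcome, the stated time point and the primary-endpoint sentence in 9.2 all use it. Carry the same definition into the synopsis and Section 3, which give no time point.
- List self-compassion and 3-month return as secondary outcomes.
- Delete the median-split phrase from 9.2.
- Keep Fisher's exact test, which 9.1, 9.2 and 9.4.2 all name, and drop logistic regression as an alternative primary test.
- Report the risk difference with a 95% CI whatever the p value.
- Restate the power in 9.2 for Fisher's test.

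Randomisation, visits and data collection do not change. The team gives up the choice of time point. The real cost is in the power statement: 19 per group gives 68%, and at least 80% needs 24 per group. That is 48 evaluable participants, which leaves 50 − 48 = 2 of the planned enrolment for attrition.
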